6.3 Labeling, Packaging, Storage, and Handling

6.3.1 Labeling

Labels containing study information are applied to the investigational product(s) container. All investigational product is labeled with a minimum of the protocol number, dosage form, directions for use, storage conditions, expiry date and batch number/packaging reference, the statements 'For clinical trial use only', and/or 'CAUTION: New Drug - Limited by Federal (or US) Law to Investigational Use', Keep out of reach of children', and the sponsor's name and address. Any additional labeling requirements for participating countries and/or controlled substances will also be included on the label.

Space is allocated on the label so that the site representative can record a unique subject identifier.

Additional labels (eg, those used when dispensing marketed product) may, on a case-by-case basis, be applied to the investigational product in order to satisfy local or institutional requirements, but must not:

- Contradict the clinical study label
- Obscure the clinical study label
- Identify the study subject by name.
- Additional labels may not be added without the sponsor's prior full agreement

6.3.2 Packaging

Investigational product is packaged in the following labeled containers:

CINRYZE will be supplied as open-label material in labeled cartons containing 1 labeled vial.

Sterile water will also be supplied as open-label material in labeled cartons containing 1 labeled vial.

Changes to sponsor-supplied packaging prior to dosing may not occur without full agreement in advance by the sponsor.

6.3.3 Storage

The investigator has overall responsibility for ensuring that investigational product is stored in a secure, limited-access location. Limited responsibility may be delegated to the pharmacy or member of the study team, but this delegation must be documented. Investigational products are distributed by the pharmacy or nominated member of the study team. The pharmacist/nominated team member will enter the unique subject number on the investigational product labels as they are distributed.

Investigational product must be stored in accordance with labeled storage conditions. Temperature monitoring is required at the storage location to ensure that the investigational product is maintained within an established temperature range. The investigator is responsible for ensuring that the temperature is monitored throughout the duration of the study and that records are maintained; the temperature should be monitored continuously by using either an in-house system, a mechanical recording device such as a calibrated chart recorder, or by manual means, such that both minimum and maximum thermometric values over a specific time period can be recorded and retrieved as required. Such a device (ie, certified min/max thermometer) would require manual resetting upon each recording. The sponsor must be notified immediately upon discovery of any excursion from the established range. Temperature excursions will require site investigation as to cause and remediation. The sponsor will determine the ultimate impact of excursions on the investigational product and will provide supportive documentation as necessary. Under no circumstances should the product be dispensed to subjects until the impact has been determined and the product is deemed appropriate for use by the sponsor.

The sponsor should be notified immediately if there are any changes to the storage area of the investigational product that could affect the integrity of the product(s), eg, fumigation of a storage room.

6.4 Drug Accountability

Investigators will be provided with sufficient amounts of the investigational product to carry out this protocol. The investigator or designee will acknowledge receipt of the investigational product, documenting shipment content and condition. Accurate records of all investigational product dispensed, used, returned, and/or destroyed must be maintained as detailed further in this section.

The investigator has overall responsibility for administering investigational product. Where permissible, tasks may be delegated to a qualified designee (eg, a study nurse) who is adequately trained in the protocol and who works under the direct supervision of the investigator. This delegation must be documented in the applicable study delegation of authority form.

The investigator or his/her designee (as documented by the investigator in the applicable study delegation of authority form) will administer the investigational product only to subjects included in this study following the procedures set out in the study protocol. Each subject will be given only the investigational product carrying his/her treatment assignment. All administered medication will be documented in the CRFs and/or other investigational product record.

No investigational product stock or returned inventory from a Shire ViroPharma, Inc.-sponsored study may be removed from the site where originally shipped without prior knowledge and consent by the sponsor. If such transfer is authorized by the sponsor, all applicable local, state, and national laws must be adhered to for the transfer.

The sponsor or its representatives must be permitted access to review the supplies storage and distribution procedures and records provided that the blind of the study is not compromised.

If the investigational product is to be destroyed by the study sites, sites must follow their own process/policy that describes such activities. All drug destruction processes will be documented and the sites must retain copies of these documents within the site regulatory binder. The sites must ensure that the clinical trial material accountability and destruction log is complete, accurate, and ready for review and/or audit at each monitoring visit.

Based on entries in the site drug accountability forms, it must be possible to reconcile investigational products delivered with those used and returned. All investigational products must be accounted for and all discrepancies investigated and documented to the sponsor's satisfaction.

6.5 Subject Compliance

All doses of investigational product will be administered to subjects at the investigational site. The pharmacist/nominated person will record details of dispensed product on the drug accountability form and the clinical staff will record details of administration of product in the subject's medical record.

7. STUDY PROCEDURES

7.1 Study Schedule

See [Table 1](#), [Table 2](#), and [Table 3](#) for study procedures. Screening procedures and timing are listed below. For detailed descriptions of each procedure, see Section [7.2 Study Evaluations and Procedures](#). See Section [7.2.3.5](#) for details on which laboratory tests are required locally in addition to those sent to the central laboratory.

7.1.1 Screening Period

Screening will occur after the biopsy diagnosis of the qualifying AMR episode and before the first dose of investigational product. Investigational product may not be administered within 7 days of kidney transplant. Submission of pathology slides/images will occur to confirm the qualifying AMR episode. Local laboratory testing at screening will be used to determine subject eligibility.

- Informed consent
- Screening registration in the IV/WR (IRT) system
- Medical history including the presence/absence of diabetes, pre-AMR creatinine and eGFR_{MDRD}
- Inclusion/exclusion eligibility
- Physical examination, including height and body weight
- Lower extremity examination, including a determination of presence or absence of unilateral calf tenderness or leg swelling; a diagnostic exam will be performed if a DVT is suspected
- Vital signs
- 12-lead electrocardiogram (ECG)
- Central Pregnancy testing (also local lab serum and urine) for female subjects of child-bearing potential
- Central Virology screen
- Central Hematology (also local hematology lab results will be used to assess subject eligibility at screening)
- Central Clinical chemistry (includes central lab testing for creatinine and BUN)
- Local Serum BUN, creatinine and eGFR_{MDRD} (at screening the first local laboratory creatinine value obtained after the biopsy that is diagnostic of AMR should be used to determine AMR severity for stratification)
- Central Proteinuria: spot urine protein, urine creatinine, and urine protein to urine creatinine ratio
- Renal allograft assessment, including: function, and failure

- Central Anti-C1 INH antibodies
- Donor-specific antibody identification. In addition to the central laboratory, per protocol this test is required to be performed locally only at screening. Eligibility will be based on the local results. If it is anticipated that the local screening DSA results will not be available within the screening period, previously obtained local DSA results, if available, can be used to assess eligibility if obtained after kidney transplant and within 30 days prior to the qualifying biopsy that is diagnostic of an AMR episode. In any instance, a local DSA test should still be performed at the time of AMR diagnosis.
- Donor-specific antibody reduction treatment and sucrose-free IVIg (plasmapheresis, plasma exchange, or immune adsorption treatments/sucrose-free IVIg may be provided as part of standard of care prior to study entry). All blood sample collections for laboratory analysis should be performed prior to receiving DSA reduction therapy, except as otherwise specified for PK/PD samples.
- Concomitant medications
- Adverse event monitoring
- EuroQoL Group 5-Dimension 5-Level Self-report Questionnaire
- Healthcare resource utilization

Once eligibility for participation in the study is determined, the subject should be randomized or registered as screen failure, as applicable, via IV/WRS (IRT). A screen failure is a subject who has given informed consent and failed to meet the inclusion and/or met at least 1 of the exclusion criteria and has not been randomized or administered investigational product(s). Subjects cannot be rescreened once they have been designated as a screen failure.

Note: In the event of new biopsy-proven acute AMR allowing retreatment, screening procedures will be completed as detailed in the screening retreatment column of [Table 1](#).

7.1.2 Investigational Product Administration Period

Subjects will be required to receive a minimum of 5 plasmapheresis, plasma exchange, or immune adsorption treatments from the time of diagnostic biopsy for qualifying episode of acute AMR through Study Day 13. Each DSA reduction treatment will be followed by sucrose-free IVIg (no less than 100 mg/kg). Additional DSA reduction treatments or sucrose-free IVIg may be administered at the discretion of the investigator per standard of care. NOTE: If plasmapheresis, plasma exchange, or immune adsorption treatment occurs on the same day as investigational product dosing, investigational product will be administered after completion of the DSA reduction therapy session and dosing of sucrose-free IVIg. See Section [7.2.3.5](#) for details on which laboratory tests are required locally in addition to those sent to the central laboratory.

7.1.2.1 Day 1

The first dose of investigational product on Day 1 should be administered as soon as possible and within 7 days after the qualifying biopsy procedure.

All blood sample collection for laboratory testing should be collected prior to receiving DSA reduction therapy (if given) except as specified for PK/PD samples.

- Inclusion/exclusion eligibility prior to first dose of investigational product
- Randomization via IV/WRS (IRT) prior to first dose of investigational product
- Physical examination, including body weight prior to first dose of investigational product
- Lower extremity examination prior to first dose of investigational product, including a determination of presence or absence of unilateral calf tenderness or leg swelling; a diagnostic exam will be performed if a DVT is suspected
- Vital signs (obtained within 30 minutes prior to investigational product administration and then between 30 minutes and 1 hour after completion of investigational product infusion)
- Pregnancy testing (with local urine test) prior to first dose of investigational product for female subjects of child-bearing potential
- Central Hematology prior to first dose of investigational product
- Central Clinical chemistry, local BUN and serum creatinine with eGFR_{MDRD} prior to first dose of investigational product
- Central lab blood collection for pharmacokinetic/pharmacodynamic analysis prior to the start of DSA reduction therapy (if done), within 15 minutes prior to the start of investigational product infusion, and 1 hour (+5 minutes) after the start of investigational product infusion
- Donor-specific antibody reduction treatment and sucrose-free IVIg (plasmapheresis, plasma exchange, or immune adsorption treatments/sucrose-free IVIg may be provided as part of standard of care prior to study entry)
- Investigational product administration (after DSA reduction therapy and sucrose-free IVIg, if done)
- Concomitant medications
- AE monitoring
- Renal allograft assessment including: function, and failure
- Subject survival status
- Healthcare resource utilization

7.1.2.2 Days 3, 5, 7, 9, and 11

- Lower extremity examination, including a determination of presence or absence of unilateral calf tenderness or leg swelling; a diagnostic exam will be performed if a DVT is suspected
- Body weight
- Vital signs (obtained within 30 minutes prior to investigational product administration and then between 30 minutes and 1 hour after completion of investigational product infusion)

- Serum BUN and creatinine with eGFR_{MDRD} (central and local laboratories) prior to investigational product administration
- For Day 7 only: Central lab blood collection for pharmacokinetic/pharmacodynamic analysis prior to the start of DSA reduction therapy (if done), within 15 minutes prior to the start of investigational product infusion, and 1 hour (+5 minutes) after start of investigational product infusion
- Donor-specific antibody reduction treatment and sucrose-free IVIg (plasmapheresis, plasma exchange, or immune adsorption treatments/sucrose-free IVIg may be provided as part of standard of care prior to study entry)
- Investigational product administration (after DSA reduction therapy and sucrose-free IVIg, if done)
- Concomitant medications
- AE monitoring
- Renal allograft assessment including: function and failure
- Subject survival status
- Healthcare resource utilization

7.1.2.3 Day 13

- Lower extremity examination including a determination of presence or absence of unilateral calf tenderness or leg swelling; a diagnostic exam will be performed if a DVT is suspected
- Body weight
- Vital signs (obtained within 30 minutes prior to investigational product administration and then between 30 minutes and 1 hour after completion of investigational product infusion)
- Central Hematology prior to administration of investigational product
- Central Clinical chemistry (includes BUN and creatinine) and local BUN and serum creatinine with eGFR_{MDRD} prior to administration of investigational product
- Central lab blood collection for pharmacokinetic/pharmacodynamic analysis prior to the start of DSA reduction therapy (if done), within 15 minutes prior to the start of investigational product infusion, and 1 hour (+5 minutes) after start of investigational product infusion
- Donor-specific antibody reduction treatment and sucrose-free IVIg (plasmapheresis, plasma exchange, or immune adsorption treatments/sucrose-free IVIg may be provided as part of standard of care prior to study entry)
- Investigational product administration (after DSA reduction therapy and sucrose-free IVIg, if done)
- Concomitant medications
- Adverse event monitoring
- Renal allograft assessment including: function and failure
- Subject survival status
- Healthcare resource utilization

7.1.3 Post-Treatment Follow-Up Period

See Section 7.2.3.5 for details on which laboratory tests are required locally in addition to those sent to the central laboratory.

7.1.3.1 Day 25 (± 48 hours)

- Lower extremity examination including a determination of presence or absence of unilateral calf tenderness or leg swelling; a diagnostic exam will be performed if a DVT is suspected
- Body weight
- Vital signs
- Central lab Hematology
- Serum BUN and creatinine with eGFR_{MDRD} (local and central laboratories)
- Central lab Proteinuria: spot urine protein, urine creatinine, and urine protein to urine creatinine ratio
- Central lab Anti-C1 INH antibodies
- Central lab Donor-specific antibody identification
- Concomitant medications
- Adverse event monitoring
- Renal allograft assessment including: function and failure
- Subject survival status
- EuroQoL Group 5-Dimension 5-Level Self-report Questionnaire
- Healthcare resource utilization
- Submission of pathology slides/images from screening qualifying AMR biopsy (if not submitted earlier, after randomization)

7.1.3.2 Month 3 (± 21 days)

- Body weight
- Serum BUN and creatinine with eGFR_{MDRD} (local and central laboratories)
- Central lab Proteinuria: spot urine protein, urine creatinine, and urine protein to urine creatinine ratio
- Central lab Anti-C1 INH antibodies
- Central lab Donor-specific antibody identification
- Concomitant medications
- Adverse event monitoring
- Renal allograft assessment including: function and failure

- Subject survival status
- EuroQoL Group 5-Dimension 5-Level Self-report Questionnaire
- Healthcare resource utilization

7.1.3.3 Month 6 (± 21 days)

- Presence/absence of diabetes
- Body weight
- Serum BUN and creatinine with eGFR_{MDRD} (local and central laboratories)
- Central lab Proteinuria: urine protein, urine creatinine, and urine protein to urine creatinine ratio
- Kidney allograft biopsy and submission of pathology slides/images
- Central lab Anti-C1 INH antibodies
- Central lab Donor-specific antibody identification
- Concomitant medications
- Adverse event monitoring
- Renal allograft assessment including: function and failure
- Subject survival status
- EuroQoL Group 5-Dimension 5-Level Self-report Questionnaire
- Healthcare resource utilization

7.1.3.4 Months 12 (± 21 days), Months 18, 24, 30, 36, 42 (all ± 28 days)

- Body weight
- Serum BUN and creatinine with eGFR_{MDRD} (local and central laboratories)
- Central lab Proteinuria: spot urine protein, urine creatinine, and urine protein to urine creatinine ratio
- Central lab Anti-C1 INH antibodies (only if antibodies are detected at the previous time point)
- Central lab Donor-specific antibody identification
- Concomitant medications
- Adverse event monitoring
- Renal allograft assessment including: function and failure
- Subject survival status
- EuroQoL Group 5-Dimension 5-Level Self-report Questionnaire
- Healthcare resource utilization

7.1.3.5 EOS Visit/Month 48 [\pm 28 days] or at patient discontinuation if after Month 6 Visit

- Presence/absence of diabetes
- Body weight
- Serum BUN and creatinine with eGFR_{MDRD} (local and central laboratories)
- Central lab Proteinuria: spot urine protein, urine creatinine, and urine protein to urine creatinine ratio
- Central lab Anti-C1 INH antibodies
- Central lab Donor-specific antibody identification
- Concomitant medications
- Adverse event monitoring
- Renal allograft assessment including: function and failure
- Subject survival status
- EuroQoL Group 5-Dimension 5-Level Self-report Questionnaire
- Healthcare resource utilization

All AEs and SAEs that are not resolved at the time of this contact will be followed to closure (see Section 8.1).

7.1.3.6 Early Discontinuation Visit: Discontinuation between End of Investigational Product Dosing (Day 13) and Month 6 (not applicable if discontinuation is from treatment only)

- Body weight
- Serum BUN and creatinine with eGFR_{MDRD} (local and central laboratories)
- Proteinuria: spot urine protein, urine creatinine, and urine protein to urine creatinine ratio
- Renal allograft biopsy and submission of pathology slides/images
- Donor-specific antibody identification
- Concomitant medications
- Adverse event monitoring
- Renal allograft assessment including: function and failure
- Subject survival status

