ⁱ Qualifying renal allograft biopsy for assessment of histologic parameters associated with AMR. In the event that the subject has a new episode of AMR as defined in Section 7.2.2.4, the subject may be retreated with the same treatment to which they were previously randomized and following the procedures outlined in Table 1, beginning at Day 1 with the exception of randomization and limited inclusion/exclusion criteria. For each biopsy, the pathology slides and images are to be submitted.

^j Blood samples for pharmacokinetic/pharmacodynamic analysis will be collected at the time points specified in Table 3.

^k If sucrose-free IVIg is administered on the same day as the screening visit, blood samples for immunogenicity should be obtained both prior to and after sucrose-free IVIg administration. Subjects where anti-C1 INH antibodies are detected will be followed until negative.

^l DSA antibody will be determined by central and local laboratory analysis at screening (for initial or recurrent episode of AMR), and only by the central laboratory at all other time points specified. DSA testing may be performed locally at other time points after screening for all clinical assessments as part of standard of care. Additional serum may be collected by the central laboratory for future antibody and titer testing.

^m Subjects will have a minimum of 5 plasmapheresis, plasma exchange, or immune adsorption treatments each followed by sucrose-free IVIg from the time of diagnostic biopsy for qualifying episode of acute AMR through Study Day 13. Plasmapheresis, plasma exchange, or immune adsorption treatments and sucrose-free IVIg may be provided as part of standard of care prior to study entry. Protocol-mandated plasmapheresis, plasma exchange, or immune adsorption treatments should be completed by Day 13. Additional DSA reduction treatments or doses of sucrose-free IVIg may be administered at the discretion of the investigator as part of standard of care.

Table 1 Schedule of Assessments (Screening through Day 25)

Study Procedure	(Screening) ^a		Investigational Product Administration Period							Post-Treatment Evaluations
	1 st Episode	Retreatment (recurrent AMR) within 180 days	Day 1 ^a	Day 3	Day 5	Day 7	Day 9	Day 11	Day 13	Day 25 (±48 hours)

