	Month 3 (±21 days) ^b	Month 6 (±21 days) ^b	Month 12 (±21 days) ^b	Month 18 (±28 days) ^b	Month 24 (±28 days) ^b	Month 30 (±28 days) ^b	Month 36 (±28 days) ^b	Month 42 (±28 days) ^b	Early Discontinuation Visit Between Day 13 & Month 6	EOS/Month 48 or at patient discontinuation if after Month 6 (±28 days) ^b
Presence/absence of diabetes		✓								✓
Body Weight	✓	✓	✓	✓	✓	✓	✓	✓	✓	✓
BUN & Serum Cr with eGFR (both central and local lab) ^c	✓	✓	✓	✓	✓	✓	✓	✓	✓	✓
Central lab Proteinuria: Spot urine protein, urine Cr and urine protein/urine creatinine ratio	✓	✓	✓	✓	✓	✓	✓	✓	✓	✓
Kidney allograft biopsy & submission of pathology slides & images ^d		✓							✓	
Central lab Immunogenicity (anti-C1 INH antibodies)	✓	✓	✓ ^e	✓ ^e	✓ ^e	✓ ^e	✓ ^e	✓ ^e		✓ ^e
Central lab DSA identification ^f	✓	✓	✓	✓	✓	✓	✓	✓	✓	✓
Concomitant medications ^g	✓	✓	✓	✓	✓	✓	✓	✓	✓	✓
Adverse event monitoring ^h	✓	✓	✓	✓	✓	✓	✓	✓	✓	✓
Renal allograft assessment	✓	✓	✓	✓	✓	✓	✓	✓	✓	✓
Subject survival status	✓	✓	✓	✓	✓	✓	✓	✓	✓	✓
EQ-5D-5L	✓	✓	✓	✓	✓	✓	✓	✓		✓
Health Resource Utilization	✓	✓	✓	✓	✓	✓	✓	✓		✓

BUN=blood urea nitrogen; C1 INH=C1 inhibitor; Cr=creatinine; DSA=donor-specific antibody; eGFR_{MDRD}=estimated glomerular filtration rate calculated by the Modification of Diet in Renal Disease; EOS=End of Study Visit; EQ-5D-5L= EuroQoL Group 5-Dimension 5-Level Self-report Questionnaire; SAE=serious adverse event; TG=transplant glomerulopathy

^a The duration of the study will be event driven, and is based upon an assumption that there will be approximately 51 all-cause graft failures including death. The trial will continue until 51 such events are accrued and adjudicated by the independent, blinded nephrology EAC. See Section 9.5.1 for additional details. However the maximum amount of time each subject will be followed in the study will be 4 years post initial treatment with investigational product. Subjects will complete visits every 6 months until the study is ended. If the study is stopped prior to the last enrolled subject completing Month 48, all subjects who have not reached Month 48 will be asked to return to the investigational site for their End of Study (EOS) visit.

^b Visit dates for each visit from Month 3 through EOS will reference back to Day 1 of study entry and will be based on calendar months. Visit windows for each visit in Table 2 will be ±21 days for Months 3, 6, and 12. Visit windows will be ±28 days for Months 18, 24, 30, 36, 42, 48, Early Discontinuation, and End of Study (EOS).

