Blood samples will be collected at screening (pre-dose sample should always be collected at screening), on Day 25, and at Months 3 and 6 for determination of anti-C1 INH antibodies. If sucrose-free IVIg is administered at the screening visit, a sample for anti-C1 INH will be collected before (pre-dose sample) and after sucrose-free IVIg administration (post-dose sample). Subjects with anti-C1 INH antibodies will be followed at the time points specified in [Table 2](#), to measure titers. For Months 12, 18, 24, 36, and 48 the test will be performed ONLY if anti-C1 INH antibodies are detected at the previous time point. For Months 3 and 6 the test will be performed for each subject. See [Table 2](#).

Pharmacokinetic/Pharmacodynamic Assessments

See section [7.2.4.1](#)

Urinalysis

A urine sample will be collected at the visits specified on [Tables 1](#) and [2](#) for the assessment of proteinuria, to include spot urine protein, urine creatinine, and urine protein to creatinine ratio.

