## 11.6      **Immunogenicity (Anti-C1 INH)**

The positive and negative counts of Immunogenicity (Anti-C1 INH) samples will be summarized by visit and treatment for the Safety Analysis Set. Baseline is defined as the last measurement before first dose of investigational product. All immunogenicity data will be listed.

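### The Early Discontinuation Visit has no anti-C1 INH sample, so a dosed subject who withdraws from the study before Day 25 has no scheduled post-product antibody result, and one who withdraws between Day 25 and Month 6 has no exit result

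*Protocol*

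**What the plan says.** Anti-C1 INH sampling is set out in Protocol 7.2.3.5.1: "Blood samples will be collected at screening (pre-dose sample should always be collected at screening), on Day 25, and at Months 3 and 6". It adds: "For Months 3 and 6 the test will be performed for each subject". After Month 6 the test is conditional on a positive result at the previous time point (7.2.3.5.1 and Table 2 footnote e).

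The exit visit before Month 6 is Protocol 7.1.3.6, headed "Early Discontinuation Visit: Discontinuation between End of Investigational Product Dosing (Day 13) and Month 6 (not applicable if discontinuation is from treatment only". It lists body weight, BUN and creatinine with eGFR, proteinuria, biopsy, DSA, concomitant medications, adverse events, allograft assessment and survival. The only antibody item is "Donor-specific antibody identification". In protocol Table 2 the row "Central lab Immunogenicity (anti-C1 INH antibodies") is ticked at Months 3 and 6, ticked with footnote e at later visits and at EOS, and blank in the Early Discontinuation column. The exit visit after Month 6 (7.1.3.5) does list the test.

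On follow-up of positive subjects, Table 1 footnote k says: "Subjects where anti-C1 INH antibodies are detected will be followed until negative". Table 2 footnote e speaks only of measuring titres.

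Antibodies to C1 INH are a safety endpoint in Protocol 9.9. SAP 11.6 says the positive and negative counts of "samples will be summarized by visit and treatment for the Safety Analysis Set". The resulting Table 14.3.6.1 is kept for the abbreviated CSR (SAP Section 20).

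**The concern.** The subjects with no exit sample are those who leave closest to exposure. The protocol tests everyone at Months 3 and 6 and lists a sample for those who leave later, yet it gives no reason for omitting one here. The visit already draws blood for the central laboratory.

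At stake is the completeness of a safety endpoint at a dose with little experience in this population: Protocol 8.2.1 cites 9 subjects. Each missing post-product result is a loss. If subjects who withdraw differ in antibody response from those who stay, the by-visit counts will not represent everyone who was dosed. SAP 11.6 does not ask for the number of dosed subjects without a post-dose result, so a reader of the table could not see the gap.

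**Working it through.** The documents state no figure for this point, so the check is a comparison of schedules.

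**1. First sample after investigational product.** Dosing ends on Day 13. The next scheduled sample is Day 25 ± 48 hours, that is Day 23 to Day 27, or 23 − 13 = 10 to 27 − 13 = 14 days after the last dose. The screening sample that 7.2.3.5.1 calls post-dose is taken "after sucrose-free IVIg administration (post-dose sample"), so it is not a post-product sample.

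**2. Is the blank cell real?** The list in 7.1.3.6 and the protocol's Table 2 agree, and 7.2.3.5.1 adds no sample at this visit. In the same Table 2 column, DSA, proteinuria and BUN/creatinine are ticked. I did not rely on the SAP copy of Table 2, because its immunogenicity row is incomplete in the text available.

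**3. What each kind of leaver contributes.**

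| Subject | Scheduled post-product results by exit | Sample at exit visit |
|---|---|---|
| Withdraws from study before Day 25 | 0 | None listed |
| Withdraws from study between Day 25 and Month 3 | 1 (Day 25) | None listed |
| Withdraws from study between Month 3 and Month 6 | 2 (Day 25, Month 3) | None listed |
| Withdraws from study after Month 6 | 3 (Day 25, Months 3 and 6), plus later conditional tests | Listed in 7.1.3.5 |
| Stops treatment only | Day 25, Months 3 and 6 as planned | Not applicable |

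The last row follows from Protocol 3.2 and 4.5: a subject who stops dosing early stays in the study and still has the Day 25 visit. A retreatment screening sample before Day 25 is a theoretical exception to the first row.

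**4. After exit.** Protocol 4.5 asks sites to seek only graft and survival status from subjects who have left, so nothing later recovers the antibody result.

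**5. Who has this visit.** The heading of 7.1.3.6 starts at Day 13. Section 3.2 and Table 2 footnote c send everyone who leaves before Month 6 to it. A subject who withdraws during dosing falls between the two.

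**6. How many.** Protocol 9.6 randomizes 112 to have 100 complete: 112 − 100 = 12 leavers, in both arms together, over follow-up of up to 4 years. The documents give no timing. The number leaving before Day 25 therefore lies between 0 and 12, and the upper end would put all planned attrition into the first 25 days. In the pilot study with the same regimen, all 18 subjects completed (Protocol 1.3.2).

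**The case against.** The strongest reply is that the obvious route to bias is largely closed. A reaction that stops dosing does not remove the antibody sample, because the subject keeps the Day 25 visit. Hypersensitivity reactions are reported throughout the study as adverse events of special interest. Few subjects should withdraw fully so early, and the result feeds a descriptive table on which no test, error rate or eligibility decision depends. All of this stands. It limits the size of the point but does not fill the gap for subjects who do withdraw from the study.

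Three stronger readings are tempting, and the documents support none of them.

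- A reader might infer that the visit contradicts Table 1 footnote k. A schedule cannot bind a subject who has withdrawn, and one exit sample would not show that a positive subject has become negative. The real inconsistency is between footnote k and Table 2 footnote e, which describe different follow-up for positive subjects.
- A reader might infer that antibody incidence will be understated by a calculable amount. The documents give neither the share leaving before Day 25 nor an antibody rate in leavers or stayers. SAP 11.6 plans counts by visit, not a cumulative incidence. Subjects who leave after Day 25 are already counted at Day 25.
- A reader might infer that the visit should also repeat the Day 25 haematology, vital signs and lower extremity examination. That is a separate matter: the Month 3 visit omits all three as well, and the exit visit keeps adverse event monitoring.

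**Conclusion.** The gap is real and consistent across Protocol 7.1.3.6, Table 2 and 7.2.3.5.1. A dosed subject who withdraws from the study before the Day 25 sample has no scheduled post-product anti-C1 INH result, and one who withdraws between then and Month 6 has no result at exit.

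Its size is modest. At most about 12 subjects are expected to leave over the whole study, and an unknown, probably small, share of them would leave before Day 25 or Month 6. If leavers resemble stayers, the cost is lost data only. If they differ, the by-visit counts are biased by an amount that cannot be derived from these documents. No efficacy conclusion is affected. The change is worth making because it is cheap and the endpoint is a named one.

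The conclusion assumes that withdrawal is from the study and not from treatment only, that the subject was dosed, and that the protocol's Table 2 is complete as read.

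**What to change.** In the protocol:

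- Add a central anti-C1 INH sample to 7.1.3.6 and to the Early Discontinuation column of Table 2, with the same change in the SAP copy of Table 2.
- State that it applies to any dosed subject who leaves the study before Month 6, and reconcile the Day 13 start in the 7.1.3.6 heading with Section 3.2 and Table 2 footnote c.
- Reconcile Table 1 footnote k with Table 2 footnote e, so that one statement says how antibody-positive subjects are followed while they remain in the study.

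In SAP 11.6, count the early discontinuation sample as a post-baseline result and report, by arm, the number of dosed subjects with no post-dose result.

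The cost is one extra tube and assay for the few early leavers, at a visit that already takes central laboratory blood, plus one line in the schedule.

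SAP Section 17 records that the study was discontinued for futility after the first interim analysis, so a new sample can no longer be collected for most purposes. The step still open for the abbreviated CSR is to state in Table 14.3.6.1 the number of dosed subjects in each arm without a post-dose antibody result. That needs no new data.
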